#### **Patient Care Implications:**

Entinostat may cause fatigue or malaise; advise patient to exercise caution while driving a vehicle or operating machinery.

Administration of entinostat is contraindicated in patients with a history of allergy to entinostat or other medications that have a benzamide structure (eg, tiapride, remoxipride, clebropride).

Careful monitoring of patients for signs of infection or reactivation of past infections is recommended, as reactivation of infection has been reported in patients treated with entinostat, in some cases without evidence of neutropenia. The clinical significance of this finding and the potential association with entinostat is unknown.

Entinostat must not be used during pregnancy or while breast-feeding. Women and men participating in entinostat clinical studies must agree to use acceptable contraceptive methods, as indicated in the clinical study protocol, during treatment and for 3 months thereafter.

#### **Availability**

Entinostat is an investigational agent supplied to investigators by the Division of Cancer Treatment and Diagnosis (DCTD), NCI.

Entinostat is provided to the NCI under a Collaborative Agreement between the Pharmaceutical Collaborator and the DCTD, NCI (see Section 13.5).

##### **8.1.2 Agent Ordering and Agent Accountability**

8.1.2.1 NCI-supplied agents may be requested by eligible participating Investigators (or their authorized designee) at each participating institution. The CTEP-assigned protocol

number must be used for ordering all CTEP-supplied investigational agents. The eligible participating investigators at each participating institution must be registered with CTEP, DCTD through an annual submission of FDA Form 1572 (Statement of Investigator), NCI Biosketch, Agent Shipment Form, and Financial Disclosure Form (FDF). If there are several participating investigators at one institution, CTEP-supplied investigational agents for the study should be ordered under the name of one lead participating investigator at that institution.

Sites may order initial agent supplies when a subject is being screened for enrollment onto the study.

Submit agent requests through the PMB Online Agent Order Processing (OAOP) application. Access to OAOP requires the establishment of a CTEP Identity and Access Management (IAM) account and the maintenance of an “active” account status, a “current” password, and active person registration status. For questions about drug orders, transfers, returns, or accountability, call or email PMB any time. Refer to the PMB’s website for specific policies and guidelines related to agent management.

8.1.2.2 Agent Inventory Records – The investigator, or a responsible party designated by the investigator, must maintain a careful record of the receipt, dispensing and final disposition of all agents received from the PMB using the appropriate NCI Investigational Agent (Drug) Accountability Record (DARF) available on the CTEP forms page. Store and maintain separate NCI Investigational Agent Accountability Records for each agent, strength, formulation and ordering investigator on this protocol.

#### 8.1.3 Investigator Brochure Availability

The current version of the IB for entinostat will be accessible to site investigators and research staff through the PMB OAOP application. Access to OAOP requires the establishment of a CTEP IAM account and the maintenance of an “active” account status, a “current” password and active person registration status. Questions about IB access may be directed to the PMB IB Coordinator via email.

## 8.2 Commercial Agents

### 8.2.1 Atezolizumab (NSC 783608)

**Other Names:** Tecentriq™, MPDL3280A

**Classification:** monoclonal antibody

**M.W.: 150 KD**

**Mode of Action:** anti-PD-L1

**Description:** Atezolizumab is a humanized IgG1 monoclonal antibody consisting of two heavy chains (448 amino acids) and two light chains (214 amino acids). Atezolizumab targets human PD-L1 and inhibits its interaction with its receptor PD-1. Atezolizumab also blocks the binding of PD-L1 to B7.1, an interaction that is reported to provide additional inhibitory signals to T cells (Butte *et al.*, 2007).

**Preparation:** The prescribed dose of atezolizumab should be diluted in 0.9% NaCl to a concentration between 3.2 mg/mL and 16.8 mg/mL and infused through an intravenous line with or without a sterile, non-pyrogenic, low-protein binding in-line filter (pore size of 0.2 or 0.22 micrometer). The IV bag may be constructed of polyvinyl chloride (PVC), polyolefin (PO), or polyethylene (PE). The prepared solution may be stored at 2°C-8°C for up to 24 hours or at ambient  $\leq$  25°C (77°F) for 6 hours. If the dose solution is stored at 2°C-8°C (36°F-46°F), it should be removed from refrigeration and allowed to reach room temperature prior to administration. This time includes storage and time for administration for infusion. Do not shake or freeze infusion bags containing the dose solution.

**Storage:** 2°C-8°C (36°F-46°F) Vial contents should not be frozen or shaken and should be protected from direct sunlight.

**Stability:** Refer to product label.

**CAUTION:** No preservative is used in atezolizumab; therefore, the vial is intended for single use only. Discard any unused portion of drug remaining in a vial.

**Route of Administration:** IV infusion

**Method of Administration:** Atezolizumab is administered as an intravenous infusion over 60 minutes. If the first infusion is tolerated, all subsequent infusions may be delivered over 30 minutes. Do not administer atezolizumab as an intravenous push or bolus. No premedication is indicated for administration of Cycle 1 of atezolizumab. Patients who experience an infusion

NCI Protocol #: 10399  
Version Date: August 17, 2021

related reaction with Cycle 1 of atezolizumab may receive premedication with antihistamines or antipyretics/analgesics (e.g. acetaminophen) for subsequent infusions.

**Potential Drug Interactions:** Cytochrome P450 enzymes as well as conjugation/glucuronidation reactions are not involved in the metabolism of atezolizumab. No drug interaction studies for atezolizumab have been conducted or are planned. There are no known interactions with other medicinal products or other form of interactions.

**Patient Care Implications:** Female patients of childbearing potential should utilize contraception and take active measures to avoid pregnancy while undergoing atezolizumab treatment and for at least 150 days after the last dose of atezolizumab.

**Agent Ordering:** Commercially supplied.

For more detailed information, please consult an atezolizumab package insert.

#### 8.2.2 Carboplatin

**Molecular Formula:** C6H12N2O4Pt

**M.W.:** 371.25

**Description:** Crystalline powder

**How Supplied:** Carboplatin for injection is supplied as a sterile pyrogen-free powder and as a 10 mg/mL aqueous solution in multi-dose vials. Carboplatin is commercially available from commercial sources.

**Storage:** Refer to the package label for storage information.

**Preparation:** Consult the carboplatin package insert for detailed formulation and storage instructions.

**Administration:** IV infusion over 30-60 minutes.

**Agent Ordering:** Carboplatin is commercially available.

For more detailed information, please consult a carboplatin package insert.

#### 8.2.3 Etoposide (NSC141540)

**Product Description:** Etoposide (etoposide) is a topoisomerase inhibitor. The chemical name for etoposide is: 4'-Demethylepipodophyllotoxin 9-[4,6-O-(R)-ethylidene- $\beta$ -Dglucopyranoside]. Etoposide is a semi-synthetic derivative of podophyllotoxin.

**Solution preparation:** Etoposide injection is available as 20 mg/mL solution for injection.

NCI Protocol #: 10399  
Version Date: August 17, 2021

Etoposide should be diluted to a maximum concentration of 0.4 mg/mL in 5% Dextrose in Water or 0.9% Sodium Chloride.

Store intact vials at 20°C to 25°C (68°F to 77°F); do not freeze. Stability of diluted solutions are concentration dependent. Precipitation may occur with concentrations >0.4 mg/mL. Following dilution with 0.9% Sodium Chloride or 5% Dextrose in Water to concentrations of 0.2-0.4 mg/mL, the drug is chemically stable for 96 and 24 hours at room temperature under normal room fluorescent light in both glass and plastic containers. Sites may follow their institutional guidelines for the preparation, storage, and stability of etoposide.

**Route of Administration:** Do not give etoposide by bolus intravenous injection. Etoposide solutions may be infused over 60 minutes. Extravasation of etoposide may result in swelling, pain, cellulitis, and necrosis including skin necrosis. Etoposide is a cytotoxic drug. Follow applicable special handling and disposal procedures. To minimize the risk of dermal exposure, use of gloves is recommended. If dermal contact occurs, immediately and thoroughly wash areas of skin contact with soap and water and flush mucosa with water

**Agent Ordering:** Commercially Supplied.

For more detailed information, please consult an etoposide package insert.

## 9. STATISTICAL CONSIDERATIONS

### 9.1 Study Design/Endpoints

This is a phase 1 trial to evaluate the safety and efficacy of various doses of entinostat combined with atezolizumab, carboplatin, and etoposide therapy for patients with treatment naïve ES-SCLC. Four dose levels of entinostat are detailed in Figure 1. The Bayesian optimal interval (BOIN) design will be used to find the maximum tolerated dose (MTD) based on safety (Liu and Yuan, 2015; Yuan et al., 2016). The target toxicity rate for the MTD is 20%. Due to overlapping hematologic toxicities between chemotherapy and entinostat, it may be difficult to separate attributions specifically to entinostat, particularly for thrombocytopenia events. Our DLT definitions will count these more extreme hematologic events at DLTs, although it is recognized that these occur in the setting of carboplatin and etoposide chemotherapy alone. Therefore, it is anticipated that a 20% DLT rate is a conservative estimate of the true DLTs directly related to entinostat. Furthermore, small cell lung cancer is an aggressive malignancy with poor overall survival. Additional toxicity is justified if there is potential for efficacy gains. Dose-limiting toxicities (DLT) will be determined by adverse events occurring during the first cycle of treatment. DLTs are defined in Section 6.2.

The primary endpoints of the study are:

- MTD of entinostat
- Grade 3/4 adverse event rate as defined by CTCAE v5.0
- Number of cycles received of the combination of entinostat, atezolizumab, carboplatin, and etoposide (maximum = 4)

The secondary endpoint of the study is:

- 9-month PFS rate, defined as the proportion of patients alive and without disease progression after 9 months from study enrollment

#### 9.1.1 Treatment allocation

Participants will be enrolled and treated in cohorts of size 3. Only DLTs that occur within the first cycle will be used for dose finding. As shown in Figure 2, the BOIN design uses the following rule, optimized to minimize the probability of incorrect dose assignment, to guide dose escalation and de-escalation.

The steps to implement the BOIN design are as follows: 1) Participants in the first cohort are treated at dose level 1; 2) To assign a dose to the next cohort of participants, conduct dose escalation and de-escalation according to the rule displayed in the table below; 3) Repeat step 2 until the maximum sample size of 36 is reached, or stop the trial if the number of participants treated at the current dose reaches 12 and the decision according to the table below is to stay at the current dose.

After the trial is completed, the MTD is determined based on isotonic regression as specified in Liu and Yuan (2015). This computation is implemented by the shiny app “BOIN” available at <http://www.trialdesign.org>. Specifically, the MTD is the dose for which the isotonic estimate of

[figure not shown]
the toxicity rate is closest to the target toxicity rate. If there are ties, the higher dose level will be selected when the isotonic estimate is lower than the target toxicity rate and the lower dose level will be selected when the isotonic estimate is greater than or equal to the target toxicity rate.

At the conclusion of the trial, all available safety data will be reviewed. If a significant number of clinically significant adverse events outside the definition of a DLT occurred at the MTD, the recommended phase 2 dose may be a lower dose level than the MTD. Examples of clinically significant events that would be considered are events similar to DLTs that occurred in later cycles outside the DLT window, treatment discontinuation due to an adverse event attributed to entinostat, or patient withdrawal from the study due to intolerable adverse events.

When using the table below, the following descriptions for decision types should be considered. “Eliminate” means eliminate the current and higher doses from the trial to prevent treating any future participants at these doses because they are overly toxic. When a dose is eliminated, automatically de-escalate the dose to the next lower level. When the lowest dose is eliminated, stop the trial for safety. In this case, no dose should be selected as the MTD. If none of the actions (i.e., escalation, de-escalation or elimination) is triggered, treat the new participants at the current dose. If the current dose is the lowest dose and the rule indicates dose de-escalation, treat the new participants at the lowest dose unless the number of DLTs reaches the elimination boundary, at which point terminate the trial for safety. If the current dose is the highest dose and the rule indicates dose escalation, treat the new participants at the highest dose.

Escalation/De-escalation Rule												
Number of patients treated	1	2	3	4	5	6	7	8	9	10	11	12
Escalate if # of DLT <=	0	0	0	0	0	0	1	1	1	1	1	1
Deescalate if # of DLT >=	1	1	1	1	2	2	2	2	3	3	3	3
Eliminate if # of DLT >=	NA	NA	2	3	3	3	4	4	4	5	5	5

Figure 2: Study Design

$$* \text{DLT rate} = \frac{\text{Total number of patients who experienced DLT at the current dose}}{\text{Total number of patients treated at the current dose}}$$

Figure 3: Study Design

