### 9.1.2 Safety

Dose elimination rules are included to provide guidance for doses with a high probability that the rate of toxicity is greater than the target toxicity rate of 20%. For the purpose of overdose control, doses  $j$  and higher levels will be eliminated from further examination if  $\Pr(p_j \geq 0.20 | \text{data}) > 0.95$  and at least 3 participants have been treated at dose level  $j$ , where  $p_j$  is the true DLT rate of dose level  $j, j=1, \dots, 3$ . This posterior probability is evaluated based on the beta-binomial model  $y_j | p_j \sim \text{binomial}(p_j)$  with  $p_j \sim \text{uniform}(0,1)$ , where  $y_j$  is the number of participants experienced DLT at dose level  $j$ . When the lowest dose is eliminated, the trial will stop for safety. The probability cutoff 0.95 is chosen to be consistent with the common practice that when the target DLT rate  $\leq 1/6$ , a dose with 2/3 participants experienced DLT is eliminated. The

above dose escalation/de-escalation and elimination rule can be equivalently presented in the dose escalation/de-escalation table in Section 9.1.1, which will be used to conduct the trial.

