## 9.2 Sample Size/Accrual Rate

The maximum sample size is 36 participants and the trial will stop accruing participants once 12 participants have been treated on a single dose level. The maximum target sample size is based on obtaining sufficient information to assess the study aim of establishing the MTD. Operating characteristics provided in the table in section 9.1.3 indicate that the sample size results in a high rate of simulated trials identifying the target dose level as the MTD across multiple dose-toxicity scenarios, highlighting the ability of study design to achieve the primary aim of determining the MTD.

We anticipate accruing 2 patients per month and therefore expect to complete accrual within 18 months.

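### Sections 9.1.1 and 9.2 state different stop rules at 12 patients per level; the published operating characteristics follow 9.1.1, under which the 12-column decision table is too short in 18–33% of simulated trials

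*Combined protocol and SAP*

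**What the plan says.** Section 9.1.1 sets cohorts of 3, starts at Level 1 and applies the printed table after each cohort. The upper limit is given as "Repeat step 2 until the maximum sample size of 36 is reached". Earlier stopping has two conditions, a count and a decision to stay: "stop the trial if the number of participants treated at the current dose reaches 12 and the decision according to the table below". If the decision at 12 is to escalate or de-escalate, accrual goes on.

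Section 9.2 gives the stop differently: "the trial will stop accruing participants once 12 participants have been treated on a single dose level". Section 9.1.3, beside the simulation results, also refers to trials ending when 12 participants have been observed on one level, with no stay condition.

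The decision table appears in 6.2 and again in 9.1.1. Its rows (the first begins "Escalate if # of DLT <=") cover 1 to 12 patients. Section 9.1.2 calls the rule equivalent to the "table in Section 9.1.1, which will be used to conduct the trial". The same section gives the elimination criterion as a formula: posterior probability above 0.95 that the DLT rate is at least 0.20, uniform prior, at least 3 treated, and no upper limit on n.

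**The concern.** In the printed n = 12 column, only 2 DLTs gives stay: 0 or 1 escalates, and 3 or more de-escalates. Under 9.1.1 a level can therefore reach 12, be left, and be revisited.

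One path by the printed table:
- Level 1 has 1/3, so the trial de-escalates; Level -1 has 0/3, so it returns.
- Level 1 then goes to 1/6 (stay), 2/9 (stay) and 3/12 (de-escalate).
- Level -1 goes to 0/6 (escalate), and the next cohort takes Level 1 to 15 patients.

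The next decision needs a column that the table does not have. At stake is the MTD, a primary endpoint. Either the tool for running the trial does not cover the design that was simulated, or the simulated design is not the trial that 9.2 describes.

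**Working it through.** **Inputs.** Target DLT rate 0.20 (9.1). Cohorts of 3, start at Level 1, maximum 36 (9.1.1). Elimination cutoff 0.95 with a uniform prior (9.1.2). Behaviour at the lowest and highest dose (9.1.1). True DLT rates by scenario (9.1.3). One assumption: the BOIN interval limits are the defaults, 0.6 and 1.4 times the target (0.12 and 0.28). The documents do not state them.

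**Step 1: reproduce the printed table.**
- Escalation cut-off: ln(0.88/0.80) / ln[(0.20×0.88)/(0.12×0.80)] = 0.0953/0.6061 = 0.157.
- De-escalation cut-off: ln(0.80/0.72) / ln[(0.28×0.80)/(0.20×0.72)] = 0.1054/0.4418 = 0.238.
- Elimination: smallest y with Pr(p ≥ 0.20) > 0.95 under Beta(1+y, 1+n−y). At n = 3, y = 2 gives 0.973 and y = 1 gives 0.819, so the limit is 2, as printed.

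All 12 printed columns are reproduced exactly, which supports the assumed multipliers.

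**Step 2: find which stop rule produced 9.1.3.** Mean N comes from exact enumeration of all trial paths for the first two rules and from 20,000 simulated trials per scenario for the third.

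| Stop rule | S1 | S2 | S3 | S4 |
|---|---|---|---|---|
| Stated in 9.1.3 | 23.7 | 23.7 | 22.3 | 19.4 |
| 9.1.1: 12 at the current dose and the next cohort would stay there | 23.6 | 23.8 | 22.3 | 19.6 |
| 9.2: 12 at any level | 20.5 | 19.7 | 18.3 | 16.6 |
| 9.1.1 read strictly: only a literal stay in the table | 28.3 | 27.7 | 26.0 | 23.0 |

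The second row counts an escalate decision at the highest available dose, and a de-escalate decision at the lowest, as stay. Under it, early safety stops are 0.07/0.30/3.5/14.6% against the stated 0.1/0.4/3.5/15.1%, and simulated selection percentages agree to within about 0.4 points. The other two rules do not reproduce the stated mean N.

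**Step 3: how often a level passes 12 under the reproducing rule (exact).**

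| | S1 | S2 | S3 | S4 |
|---|---|---|---|---|
| More than 12 at some level | 25.8% | 32.7% | 29.3% | 17.9% |
| Dose decision at n > 12 with total below 36 | 24.7% | 31.6% | 28.6% | 17.6% |

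The largest n at one level is 21. Under the 9.2 rule both rows are 0%.

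**Step 4: the missing columns, by the same formulas.**

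| n | 0.157n | 0.238n | Escalate ≤ | De-escalate ≥ | Eliminate ≥ (posterior probability at limit; one DLT fewer) |
|---|---|---|---|---|---|
| 15 | 2.36 | 3.58 | 2 | 4 | 6 (0.973; 0.918) |
| 18 | 2.83 | 4.29 | 2 | 5 | 7 (0.977; 0.932) |
| 21 | 3.30 | 5.01 | 3 | 6 | 8 (0.980; 0.944) |

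The products use the unrounded cut-offs 0.15724 and 0.23846.

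**Step 5: a hypothetical.** If a team carried column 12 forward, it would stay at 2/15, de-escalate at 3/15 (exactly the 20% target) and eliminate at 5/15. In 60,000 simulated trials per scenario, selection of the target level would fall from 48.7 to 45.4% (S1), 38.8 to 36.1% (S2) and 45.0 to 42.0% (S3), and selection of Level -1 in S3 would rise from 29.5 to 35.3%. In S4, where Level -1 is the target, a separate 20,000-trial run shows correct selection rising from about 52 to 56%. The effect is a downward shift in dose, not a uniform loss.

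**The case against.** The strongest reply is that 9.2 stops accrual at 12 on any level, so no level passes 12 and the table is complete. That is right about 9.2. But the figures in 9.1.3 are then not those of the trial to be run, so the reply moves the inconsistency without removing it.

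A reader might infer that no rule at all exists beyond 12, and that safety elimination would be undefined in up to a third of trials. The documents do not support this. The criterion in 9.1.2 holds for any n of at least 3, and the elimination limits above come from it. Only escalation and de-escalation cut-offs are absent from the readable text. Even that absence is not certain: Figures 2 and 3 are not visible, and a surviving note defines the DLT rate at the current dose, so they may show rate cut-offs valid at any n.

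A reader might also take the selection losses in Step 5 as the expected harm. They assume that column 12 is reused, and no text instructs this. Column 12 would give a different action at some point in about 19/25/23/14% of trials, and a different elimination decision in only 4/7/9/7%.

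**Conclusion.** The concern holds as an inconsistency between the two stop rules, and neither reading leaves the plan consistent. Under 9.1.1 the decision table lacks columns that 18–33% of simulated trials would enter. Under 9.2 the table suffices, but 9.1.3 overstates mean N by 2.8 to 4.0 patients (19.4 − 16.6 in S4; 23.7 − 19.7 in S2). Selection figures also move: in S4 the target level is chosen in about 42.9% of trials under the 9.2 rule, against the stated 51.73%.

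This rests on the 0.6 and 1.4 multipliers, which are inferred from the exact match with the printed table, and on the effective reading of stay at the dose limits, which is inferred from the match with 9.1.3. It does not establish that the full document lacks cut-offs beyond 12, because two figures cannot be seen. The point should be settled before the table is used: it bears on dose assignment and on the primary endpoint.

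**What to change.** State one stop rule, in the same words, in 9.1.1, 9.1.3 and 9.2.

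- **If 9.1.1 governs:** correct the 9.2 wording and say that an escalate decision at the highest available dose, and a de-escalate decision at the lowest, count as stay. Extend both copies of the table (6.2 and 9.1.1) to n = 15, 18 and 21 (escalate ≤ / de-escalate ≥ / eliminate ≥: 2/4/6, 2/5/7, 3/6/8), after confirming the multipliers. Alternatively, print the cut-offs 0.157 and 0.238 beside the formula in 9.1.2. Larger columns are not needed, because no level passes 21. If Figures 2 or 3 already show the cut-offs, a cross-reference is enough.
- **If 9.2 governs:** remove the stay condition from 9.1.1, leave the table as it is, and rerun and restate 9.1.3.

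The first option costs a text edit and three columns in two tables. The second costs a text edit and one rerun of the simulations. Neither changes the sample-size ceiling of 36.
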